9 INVESTIGATIONAL PLAN

9.1 Overall Study Design and Plan

This is a multicenter, randomized, double-blind, placebo-controlled, parallel-group study in obese adolescents ages 12 to 17 years. Approximately 260 subjects will be randomized in a 1:1 ratio to Belviq XR 20 mg QD (130 subjects) and placebo (130 subjects). Subjects will be stratified by sex. Subjects will receive Belviq XR 20 mg or matched placebo QD in a 1:1 ratio for up to 52 weeks. A recruitment plan will be developed to ensure at least 20% of younger subjects (12 to 13 years of age) are enrolled in the study. Throughout the duration of the study, subjects will be encouraged to adhere to a lifestyle modification program that includes a standardized, age-appropriate diet and exercise counseling (see [Appendix 2](#)). (revised per Amendments 02 and 03)

The study will consist of 2 phases: Prerandomization and Randomization. The Prerandomization Phase will last up to 30 days and consists of 1 visit during which subjects will be screened for eligibility. The Randomization Phase consists of a Treatment Period and a Follow-Up Period. The Treatment Period will last for a maximum of 52 weeks, with visits at Weeks 1, 5, 8, 12, 20, 28, 36, 44, and 52; the Follow-Up Period will extend from the End of Treatment (EOT) visit to the End of Study (EOS) visit.

Subjects who screen fail can be rescreened only once. All subjects will continue in the study until the 52-week evaluation is completed. Subjects who discontinue treatment prematurely will be followed up until study completion. All attempts will be made to capture height and weight in all subjects whether or not they are still on study drug at the end of the study. (revised per Amendments 03 and 04)

Study sites will be selected to ensure adequate representation of adolescents of ethnic and racial minorities. (revised per Amendment 03)

A Data Monitoring Committee (DMC) will be established to monitor and conduct periodic safety review of unblinded data. DMC members will be chosen based on their expertise in evaluating these clinical events. A separate DMC charter will be established. (revised per Amendment 03)

9.1.1 Prerandomization Phase

Screening will occur during the Prerandomization Phase at Visit 1.

9.1.1.1 Screening Period

The purpose of the Screening Period is to obtain the informed consent and assent and to establish protocol eligibility. Procedures to be followed when obtaining informed consent are detailed in [Section 5.3](#). Careful initial screening is important in the recruitment of families who both fully understand the requirements of this 1 year, randomized, controlled trial and are truly interested in participation. Interested caregivers and adolescents will be screened by phone to assess preliminary entry criteria. Candidates will be given a brief

description of the program and general study requirements, with an adolescent and a caregiver who is willing to participate. If preliminary entry criteria are met, adolescents and their caregivers will be invited to an initial in-clinic meeting to further discuss the study. A complete description of the study including assessments, the number of visits, the lifestyle program, the fact that the adolescent would be taking either the study drug or a placebo, the duration of the study, and the necessity of having an adolescent wishing to participate as well as a participating caregiver will be described. Consent and assent will be obtained and copies of the signed forms will be provided to families. The importance of the study and its scientific merit will be discussed. Ineligible adolescents will be referred to local weight management resources. Screening period assessments and timing thereof are shown in [Section 9.5.2](#).

9.1.2 Randomization Phase

The Randomization Phase will consist of 2 periods: the Treatment Period and the Follow-Up Period. The Treatment Period assessments and timing thereof are shown in [Section 9.5.2](#).

9.1.3 Extension Phase

Not applicable

9.2 Discussion of Study Design, Including Choice of Control Groups

The proposed dose and dosing frequency of Belviq XR in this study is 20 mg QD. The PK parameters of a single 10-mg dose of Belviq were evaluated in healthy, adolescent obese subjects in Study APD356-025. Overall, the PK parameters of Belviq and its main metabolites, M1 and M5, were similar to those in adults. Following a single, oral administration of Belviq 10 mg to a total of 8 healthy adolescent (ages 12 to 17 years old) obese subjects, the mean maximum concentration observed and the area under the concentration-time curve from time zero to infinity ($AUC_{(0-inf)}$) were 36.5 ng/mL and 464 hr \times ng/mL, respectively. The mean Belviq terminal phase half-life was 9.70 hours, similar to that observed in adults, thus supporting a similar dosing frequency (QD) in adolescent subjects.

Additionally, a single dose PK study in 8 healthy obese pediatric subjects ages 6 to 11 years of age was performed. The PK analysis after a single 10-mg dose of lorcaserin revealed that the lorcaserin $AUC_{(0-inf)}$ values tended to increase with decreasing body weight and age. However, the body weight normalized $AUC_{(0-inf)}$ values were similar across the age groups, therefore the data indicated no effect of age on the lorcaserin PK. Integrated assessment of the PK versus body weight relationship, pooling the data from pediatric and adult subjects from previous studies, suggested that the lorcaserin area under the curve values for subjects with body weight of at least 60 kg overlapped with the area under the curve values from adolescents and adults. Therefore, no dose adjustment relative to adults and adolescents is deemed necessary for pediatric or adolescent subjects with a body weight of at least 60 kg.

Based on CDC growth charts, the likelihood of subjects who are older than 12 years of age having a body weight of less than 60 kg is very low; therefore, the current study as designed

to enroll subjects between 12 to 17 years of age with body weight at least 60 kg, will cover majority of the population of interest. The targeted study population comprises 260 obese adolescents 12 to 17 years of age, with a body weight at least 60 kg. (revised per Amendment 02)

Obese adolescents will be identified using gender- and age-specific BMI measurement. Obesity in adolescents is defined by US Expert committee recommendations as BMI in or above the 95th percentile ([Barlow, 2007](#)).

Randomization will be used in this study to avoid bias in the assignment of subjects to treatment, to increase the likelihood that known and unknown subject attributes (eg, demographics, baseline characteristics) are balanced across treatment groups, and to ensure the validity of statistical comparisons across treatment groups. Blinding to treatment will be used to reduce potential bias during data collection and evaluation of endpoints.

9.3 Selection of Study Population

Approximately 500 subjects will be screened to ensure that 260 subjects will be randomized. (revised per Amendment 02)

Subjects who do not meet all inclusion criteria or do meet any exclusion criteria will not be eligible to receive study drug. Subjects who screen fail can be rescreened only once and without repeating the screening echocardiogram for up to 90 days after the previous echocardiogram. All other screening assessments must be repeated when a subject is rescreened. Subjects that rescreen more than 90 days after the previous echocardiogram must repeat all screening assessments including the screening echocardiogram. (revised per Amendments 03 and 04)

9.3.1 Inclusion Criteria

Subjects must meet all of the following criteria to be included in this study:

1. Healthy male or female adolescents, ages 12 to 17 years old (inclusive) at Screening, with an initial BMI that is greater than or equal to the United States (US)-weighted mean of the 95th percentile based on age and sex with a body weight greater than 60 kg. Subjects with T2DM may have a pre-existing or new diagnosis of T2DM.

Subjects with pre-existing T2DM should have prior documentation consistent with the diagnosis and/or be on active pharmacotherapy for T2DM.

Subjects with a new diagnosis of T2DM (ie, diagnosed at Screening) should be based on the 2016 American Diabetes Association (ADA) guidelines. The diagnostic criteria are met if a subject has unequivocal hyperglycemia (random plasma glucose ≥ 200 mg/dL (11.1 mmol/L) with classic symptoms of hyperglycemia or hyperglycemic crisis) OR any of the following criteria are observed and then confirmed:

- o HbA1c $\geq 6.5\%$
- o fasting plasma glucose (FPG) ≥ 126 mg/dL (7.0 mmol/L)

- o 2-hour plasma glucose ≥ 200 mg/dL (11.1 mmol/L) by an oral glucose tolerance test (OGTT)

All T2DM subjects must have an HbA1c $< 10\%$ at Screening. If subjects are being or need to be treated with antidiabetic agents, the T2DM treatment regimen must be stable for at least 3 months before randomization. A single rescreen is allowed following stabilization. Stable control refers to minimal dose changes to existing medications for glycemic control and no medications being initiated for glycemic control in the 3 months before Randomization. Minimal changes are defined as a change without any change in dose frequency, no add-on or discontinuation of other antidiabetic agents, and the subject has not been hospitalized due to hypo- or hyperglycemic events. (revised per Amendment 03)

2. Subjects and their families are not planning to move away from the area for the duration of the study
3. Able and willing to comply with all aspects of the study, including a standardized, reduced-calorie diet and an age-appropriate, increased physical activity program
4. Considered in stable health in the opinion of the investigator
5. Caregivers or guardians meet the following requirements:
 - a. Able and willing to support and supervise study participation in the opinion of the investigator, including consideration of any existing physical, medical, or mental condition that prevents compliance with the protocol
 - b. Able and willing to personally comply with and execute all aspects of the study requirements for the caregivers or guardians

9.3.2 Exclusion Criteria

Subjects who meet any of the following criteria will be excluded from this study:

1. Clinically significant new illness within 1 month before randomization that may affect the subject's ability to fulfill the study requirements or significantly confound the assessments
2. Who cannot swallow investigational products
3. With T2DM who have hypoglycemia unawareness (revised per Amendment 03)
4. Any of the following findings on screening echocardiography:
 - Aortic regurgitation mild or greater
 - Mitral regurgitation moderate or greater
 - Mitral or aortic valve stenosis greater than mild (ie, aortic stenosis [AS]: jet > 3.0 m/s, mean gradient > 25 mm Hg, and aortic valve area [AVA] < 1.5 cm²; MS: mean gradient > 5 mm Hg and mitral valve area [MVA] < 1.5 cm²)
 - Systolic pulmonary artery pressure (SPAP) > 40 mm Hg (and/or tricuspid regurgitation (TR) jet velocity > 2.9 m/s)
 - In cases where an actual SPAP value is not measurable due to lack of adequate TR jet, the pulmonary flow acceleration time measured at the right ventricular outflow tract (RVOTAT), will be used to assess eligibility. Subjects with a

RVOTAT \leq 100 msec will be excluded, suggesting an elevated mean SPAP; eligibility for the those subjects with RVOTAT between 100 and 120 msec will be determined based on combined assessment of the TR jet, septal motion and right ventricular size.

- Left ventricular ejection fraction $<45\%$
 - Intracardiac mass, tumor or thrombus
 - Evidence of congenital heart disease
 - Clinically significant pericardial effusion (eg, moderate or larger or with hemodynamic compromise)
5. Significant renal or hepatic disease as evidenced by a serum creatinine greater than $1.5 \times$ upper limit of normal (ULN), serum transaminases greater than $3 \times$ ULN, or total bilirubin greater than $1.5 \times$ ULN in absence of Gilbert's syndrome
 6. Any suicidal ideation with intent with or without a plan, at the time of or within 6 months of Screening, as indicated by answering "Yes" to questions 4 or 5 on the Suicidal Ideation section of the C-SSRS
 7. Any suicidal behavior in the past based on the C-SSRS (revised per Amendment 01)
 8. Any history of anorexia or bulimia within 2 years before Screening, Attention Deficit Hyperactivity Disorder (ADHD), any Diagnostic and Statistical Manual of Mental Disorders, 5th Edition (DSM-5) depressive disorder, bipolar disorder, or schizophrenia
 9. Known secondary causes (genetic, endocrine, or metabolic) for obesity (eg, Prader-Willi syndrome, Bardet Biedl syndrome, Down's Syndrome, untreated hypothyroidism, Cushing's syndrome, daily systemic corticosteroid exposure for longer than 30 days, history of significant exposure to corticosteroids for chronic illness during the past year; inhaled steroids will be allowed) (revised per Amendment 03)
 10. Use of other products intended for weight loss including prescription drugs, over-the-counter (OTC) drugs, and herbal preparations within 1 month before Screening
 11. Use of any of the following medications:
 - a) Serotonergic drugs within 7 days (or 5 half-lives, whichever is longer) or monoamine oxidase inhibitors (MAOIs) within 30 days before Randomization, including:
 - selective serotonin reuptake inhibitors (SSRIs)
 - serotonin norepinephrine reuptake inhibitors (SNRIs)
 - tricyclic antidepressants (TCAs)
 - bupropion
 - triptans
 - St. John's Wort
 - tryptophan
 - linezolid
 - dextromethorphan in any form (eg, OTC cold medicines)
 - lithium
 - tramadol
 - antipsychotics or other dopamine antagonists

- b) Others
- antiseizure medications including valproic acid, zonisamide, topiramate and lamotrigine
 - oral steroids (topical and inhaled steroids are acceptable)
 - stimulant medications (Ritalin®, Concerta®, biphedamine and Dexedrine®)
 - benzodiazepines
12. Use of drugs known to increase the risk for cardiac valvulopathy within 6 months before Screening, including but not limited to pergolide, ergotamine, methysergide, and cabergoline
 13. History or evidence of clinically significant disease (eg, malignancy, cardiac, respiratory, gastrointestinal, renal, or psychiatric disease) other than prediabetes (impaired fasting glucose or impaired glucose tolerance), T2DM treated with oral antidiabetic agents (excluding sulfonylurea) or non-insulin injectable antidiabetic agents, obstructive sleep apnea, dyslipidemia, and nonalcoholic fatty liver disease
 14. Use of Belviq XR within 6 months before Screening or hypersensitivity to Belviq XR or any of the excipients
 15. Significant change in diet or level of physical activity within 1 month before dosing or change in weight of more than 5 kg within 3 months before Screening
 16. Any use of a of very-low-calorie (<1000 calories/day) weight loss diet within 6 months before Screening
 17. History of alcohol or drug dependence or abuse
 18. Recreational drug use within 2 years before Screening
 19. Known to be human immunodeficiency virus (HIV) positive
 20. Known to have active viral hepatitis (B or C) (revised per Amendment 01)
 21. Malignancy within 5 years before Screening
 22. Unable to attend scheduled visits (eg, lack of transportation) or lack of a caregiver or guardian to supervise study participation
 23. Special needs subjects who are unable to comprehend study-related instructions (eg, mild to profound mental retardation [IQ <70], moderate to severe cognitive developmental delay, pervasive development disorders, autism)
 24. Ongoing epilepsy or other seizure disorder, or use of medications for a seizure disorder within 6 months of screening or any time between screening and randomization
 25. Subjects with a BP in the 95th percentile or greater for age, sex, and height on 2 separate readings recorded on 2 separate days. Those subjects who had uncontrolled hypertension at Screening can be rescreened more than 1 month after initiation or adjustment of antihypertensive therapy 1 time.
 26. Currently enrolled in another clinical study or has used any investigational drug or device within 30 days before providing informed consent

27. Planned bariatric surgery during the study or prior bariatric surgical procedures (revised per Amendment 03)
28. Not suitable to participate in the study in the opinion of the investigator, including consideration of any existing physical, medical, or mental condition that prevents compliance with the protocol
29. Female subjects who are breastfeeding or pregnant at Screening or Baseline (as documented by a positive β -human chorionic gonadotropin test). A separate Baseline assessment is required if a negative screening pregnancy test was obtained more than 72 hours before the first dose of study drug.
30. Female subjects of childbearing potential who:
 - a. Had unprotected sexual intercourse within 30 days before study entry and who do not agree to use a highly effective method of contraception (eg, total abstinence, an intrauterine device, a double-barrier method [such as condom plus diaphragm with spermicide], a contraceptive implant, an oral contraceptive, or have a vasectomized partner with confirmed azoospermia) throughout the entire study period and for 28 days after study drug discontinuation
 - b. Are currently abstinent, and do not agree to use a double-barrier method (as described above) or refrain from sexual activity during the study period and for 28 days after study drug discontinuation
 - c. Are using hormonal contraceptives but are not on a stable dose of the same hormonal contraceptive product for at least 4 weeks before dosing and who do not agree to use the same contraceptive during the study and for 28 days after study drug discontinuation

(NOTE: All female subjects will be considered to be of childbearing potential unless they have been sterilized surgically [ie, bilateral tubal ligation, total hysterectomy, or bilateral oophorectomy, all with surgery at least 1 month before dosing]).

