9.5.4.2 Reporting of Pregnancy and Exposure to Study Drug through Breastfeeding

Any pregnancy in which the estimated date of conception is either before the last visit or within 28 days of last study treatment or any exposure to study drug through breastfeeding during study treatment or within 28 days of last study treatment must be reported.

If an adverse outcome of a pregnancy is suspected to be related to study drug exposure, this should be reported regardless of the length of time that has passed since the exposure to study treatment.

A congenital anomaly, death during perinatal period, an induced abortion, or a spontaneous abortion are considered to be an SAE and should be reported in the same time frame and in the same format as all other SAEs (see [Section 9.5.4.1](#)).

Pregnancies or exposure to study drug through breastfeeding must be reported by fax or email as soon as possible but no later than 1 business day from the date the investigator becomes aware of the pregnancy. The contact information for the reporting of pregnancies and exposure to study drug through breastfeeding is provided in the Investigator Study File. The Pregnancy Report Form must be used for reporting. All pregnancies must be followed to outcome. The outcome of the pregnancy must be reported as soon as possible but no later than 1 business day from the date the investigator becomes aware of the outcome.

A subject who becomes pregnant must be withdrawn from the study.

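### Exclusion No. 30 needs two conditions at once, so some sexually active females who refuse contraception for the study stay eligible

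*Protocol*

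**What the plan says.** Section 9.3.2 opens with the rule that governs the whole list: "Subjects who meet any of the following criteria will be excluded from this study". No. 30 then applies to females of childbearing potential and has three sub-items, each built from a status and a refusal.

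- 30a: "Had unprotected sexual intercourse within 30 days before study entry and who do not agree to use a highly effective method of contraception", with a list of accepted methods, for the study and 28 days after study drug ends.
- 30b: "Are currently abstinent, and do not agree to use a double-barrier method" or to refrain from sexual activity over the same period.
- 30c: "Are using hormonal contraceptives but are not on a stable dose of the same hormonal contraceptive product for at least 4 weeks before dosing"; a second condition, a refusal to stay on that product over the same period, is again attached by *and*.

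The NOTE after No. 30 sets its reach: "All female subjects will be considered to be of childbearing potential unless they have been sterilized surgically". The Synopsis repeats No. 30 with the same logic, so neither place corrects the other.

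**The concern.** The three sub-items look like a sorting of females into sexually active, abstinent and hormonal users, with an agreement asked of each group. In 30b this works, because abstinence only names the group. In 30a and 30c the first condition does more than name a group: it narrows it. The word *unprotected* in 30a leaves out those whose recent intercourse was protected. The instability condition in 30c leaves out users on a stable regimen. A female who falls outside both, and is not abstinent, is never asked by No. 30 to agree to anything.

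Treatment lasts up to 52 weeks in a population where almost every female counts as of childbearing potential. The first thing at stake is fetal exposure to study drug. The second is data: Section 9.5.4.2 states "A subject who becomes pregnant must be withdrawn from the study", and Section 9.5.5 says removed subjects may not be replaced. If the Week 52 value is then missing, the subject counts as a treatment failure in the key secondary analysis and needs imputation in the primary analysis (Section 9.7.1.6).

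**Working it through.** The plan gives no figure here to reproduce. The check is one of logic.

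**Rule.** Because meeting any one criterion excludes:

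excluded by No. 30 = (unprotected intercourse within 30 days AND refuses) OR (currently abstinent AND refuses) OR (hormonal user, not stable for 4 weeks, AND refuses).

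**Subjects who refuse.** Set every refusal term to true and cross three activity states with three hormonal states. The middle row is a sexually active female with no unprotected intercourse in the past 30 days.

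| Activity | No hormonal method | Stable hormonal | Hormonal, not stable |
|---|---|---|---|
| Unprotected within 30 days | excluded (30a) | excluded (30a) | excluded (30a, 30c) |
| Active, none unprotected within 30 days | **not excluded** | **not excluded** | excluded (30c) |
| Currently abstinent | excluded (30b) | excluded (30b) | excluded (30b, 30c) |

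Excluded: 3 + 1 + 3 = 7 of 9. Not excluded: 9 − 7 = 2 of 9. These are counts of profiles, not of subjects.

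**Subjects who agree.** Set every refusal term to false. All three sub-items become false whatever the first condition says. A hormonal user with less than 4 weeks on her product who agrees to continue is therefore eligible, and the stability condition excludes nobody who agrees. Among refusers it decides the outcome in one cell only, the right-hand cell of the middle row. There an unstable user is excluded while a stable user giving the same refusal is not.

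**Other barriers to entry or continued exposure.**

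- No. 28 excludes a subject "Not suitable to participate in the study in the opinion of the investigator". This is discretion, not a contraception requirement.
- No. 29 excludes pregnancy or breastfeeding at Screening or Baseline, with a repeat pregnancy test if the negative one is more than 72 hours old at first dose. It addresses the state at entry, not prevention afterwards.
- Urine pregnancy tests are scheduled at every visit (Section 9.5.1.6.1 and Table 2). They detect pregnancy after it has begun, and from Week 12 the clinic visits are 8 weeks apart (12, 20, 28, 36, 44, 52).
- Inclusion No. 3 asks for willingness to comply with the study, but within the protocol at hand a contraception requirement for entry appears only in No. 30.

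None of these excludes the two profiles by rule.

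**The case against.** The strongest reply is that the gap is narrow and that most of the obvious risk is already caught. That stands. A reader might infer that any sexually active female who refuses contraception can enter. The text does not support this: recent unprotected intercourse with refusal is excluded by 30a, and an abstinent refuser is excluded by 30b whatever her hormonal use.

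It is also fair to say that declining to continue the same product is not refusing all contraception. A stable hormonal user who moves to another method listed in 30a poses no gap; only one who refuses contraception altogether does.

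A reader might further take the 4-week stability condition as plainly intended to stand alone. The protocol does not say so, and 30a accepts an oral contraceptive with no prior period of stability. What can be said is only that, as worded, the condition has no effect on those who agree.

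Nor is No. 30 the only safeguard against fetal exposure. No. 29 guards entry, and testing with withdrawal limits the duration of exposure. No. 30 is the only entry rule in the protocol that concerns contraception.

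Finally, intent is partly inferred. The NOTE defines childbearing potential; it does not itself require contraception of everyone. The consent pages are not available, so whether consent asks for it cannot be checked. A careful investigator may infer the purpose or use No. 28. Eligibility should not rest on that, since a site following the text could enrol these subjects without a deviation.

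**Conclusion.** The point holds in a limited form. On the literal text, two of nine refusing profiles are not excluded: a sexually active female with no unprotected intercourse in the past 30 days who refuses contraception for the study and who either uses no hormonal method or is on a stable one. The stability condition in 30c excludes nobody who agrees to continue.

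This rests on reading *and* as a joint condition, on the rule that any one criterion excludes, and on taking refusal as refusal of every option offered.

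The number of subjects concerned cannot be derived. If half of the 260 randomized were female (an assumption), 260 / 2 = 130 would be enrolled under the rule. A reader might take that as the number affected, but it is only the number to whom No. 30 applies. Sample size, power and alpha do not change. The case for acting rests on subject safety and on the low cost of the repair.

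**What to change.** Reword No. 30 in Section 9.3.2 and in the Synopsis, identically, so that sexually active females whose recent intercourse was protected, and users on a stable hormonal regimen, fall under a limb that addresses agreement to contraception. State explicitly whether the two conditions in 30a, and the two in 30c, are joint or separate. The sponsor should reconcile the limbs with the coverage it intends; this review does not propose which contraception or stability rule is right, and the lists of accepted methods can stay as they are.

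The cost is a wording amendment, alignment of the screening checklist and consent, and possibly a few more screen failures.
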